8.2.3. Survival Graphs

The survival data will be plotted as either Kaplan-Meier or cumulative incidence distribution estimates depending on the amount of competing events. The cumulative incidence estimates and not the Kaplan-Meier estimates will be plotted if the percent of subjects with competing events in either arm exceeds 3%. When there are competing events then the Kaplan-Meier estimate is not an estimate of the probability free of event: Gooley et al, 1999.

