8.2.1. Imputation of Missing Efficacy Data

In general, there will be no imputation of missing data in efficacy analyses other than the primary endpoint (overall survival).

Imputation of the primary endpoint may depend on the date of the first occurrence of an event associated with the endpoint. When the event has yet to occur the analysis will nonetheless require an analytical date be available for the analysis. These are known as censored or truncated dates. A censored date is the date of the most recent assessment for the event for a subject for which the event of interest has yet to occur and for which additional time may lead to observation of the event of interest. A truncated date is the date of a competing event that precludes the observation of the event of interest. The distinction between designating an analytical date as censored or truncated will depend on the purpose of the analysis and will be designated for each analysis. For example, if death is the event of interest and a subject is still alive and being followed for the date of death then the date last known alive is a censored date, whereas the date a subject withdraws consent for continued follow-up of vital status (a competing event) is a truncated date. The nature of the competing event will dictate whether the

competing event is permanent. For example, the date of death for a subject who has withdrawn consent may later become known passively from governmental death records.

Dates associated with the primary endpoint with missing day of the month will be completed by imputing the missing day of the month as the 15th day of that month, provided another date to be used in the computation of an interval is not in the same month. If the day of the month is missing and the other date is in the same month, then the missing day of the month will be taken as half the distance to the beginning or end of the month (depending on expected sequence). If both dates to be used in the computation of an interval are missing day of the month then an interval of 15 days (plus or minus) will be used.

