8.2.2. Survival Analysis Method

Imputation of missing date parts will follow the rules previously specified. Competing events for death are “definite” lost to follow-up and withdrawal of consent for continued vital status assessments. Both of these competing events are subject to revision for an individual subject with the passage of time.

The primary analyses will be performed on the ITT set and will analyze subjects according to the randomized arm. The primary analysis will be repeated on the FAS as a sensitivity analysis.

The primary test of each endpoint will consist of a stratified logrank test for the test of the null hypothesis (STRATA <stratification-variable> / TEST=LOGRANK;). See [Section 4.2](#) for the definition of the stratification variable. The significance of the logrank test will be assessed by referring the one-sided stratified logrank test P_1 to 0.0125, and the comparison will be said to meet statistical criterion if $P_1 < 0.0125$.

Notes:

- These analyses must be stratified: Anderson et al. 2006.
- When there are competing events then censoring competing events provides a between-arm test of the event of interest: Prentice et al. 1978.

The hazard ratio for each comparison will be estimated using stratified (STRATA <stratification-variable>;) proportional hazard regression with the specification of ties handled by the exact method (TIES=EXACT option on MODEL statement). Two-sided 95% confidence interval will be reported in order to maintain consistency with the reporting of estimates from other prostate cancer studies.

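### The survival figure switches to cumulative incidence when more than 3% of an arm is lost or withdraws consent, which treats censoring as a competing risk and overstates survival

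*SAP*

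**What the plan says.** SAP 3.2.1 defines overall survival as time from randomisation to death from any cause. It lists death, competing event and censoring as three separate ways for a man's time to end.

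SAP 8.2.2 names the competing events for death as definite "lost to follow-up and withdrawal of consent for continued vital status assessments". It adds: "Both of these competing events are subject to revision for an individual subject with the passage of time". For the primary test it notes: "When there are competing events then censoring competing events provides a between-arm test of the event of interest".

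SAP 8.2.1 gives the underlying definition: "A truncated date is the date of a competing event that precludes the observation of the event of interest". Its example sets a man still in follow-up, who is censored, against a man who withdraws: "whereas the date a subject withdraws consent for continued follow-up of vital status (a competing event) is a truncated date". It then accepts that "the date of death for a subject who has withdrawn consent may later become known passively from governmental death records".

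SAP 8.2.3 sets the plotting rule: "The cumulative incidence estimates and not the Kaplan-Meier estimates will be plotted if the percent of subjects with competing events in either arm exceeds 3" per cent. The reason given is: "When there are competing events then the Kaplan-Meier estimate is not an estimate of the probability free of event".

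Protocol 9.1 has no competing events. A man not known to have died contributes time to the date he was last known alive, and that time is called censored.

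**The concern.** A competing risk is an event after which the event of interest can no longer happen. When the endpoint is death from any cause, no such event exists. Loss and withdrawal end observation, not the possibility of dying, and SAP 8.2.1 says as much when it expects some of these deaths to turn up in records. The argument against Kaplan-Meier in 8.2.3 is correct for genuine competing risks but does not apply to these two events.

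A cumulative incidence curve with loss as a competing cause estimates the probability of dying while still under observation. Lost men stay in the denominator but are not counted as deaths unless they are later reclassified, so one minus that curve lies above true survival. (The SAP does not say whether the curve or its complement will be drawn. The deaths are understated by the same amount either way.)

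At stake is the main display of absolute benefit on the sole primary endpoint. It would treat the same men differently from the logrank test and the Cox model. It would also differ from the graphs in SAP 8.2.4, 8.5.1 and 8.5.3, which stay Kaplan-Meier whatever the loss.

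**Working it through.** **Inputs from the documents.** Control median 22 months, hazard 0.3781 per year, three-year survival 32.2% (SAP 4.1.1); 400 men per arm, 30-month accrual with a 19-month ramp, final analysis at 5.1 years (SAP 4.1.5); ramp slope 3.08 per month (SAP Appendix B).

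**Assumptions.** The documents give no loss rate, so 3%, 5% and 10% are illustrative. The loss hazard *m* is constant and independent of death, and no deaths are recovered later.

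**Plan's own figure.** ln 2 ÷ (22/12) = 0.3781 per year, and exp(−3 × 0.3781) = 0.322. Both match SAP 4.1.1.

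**Trigger.** 3% of 400 is 12, so the 13th such man in an arm of 400 switches the plot.

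**Formulas**, with λ = 0.3781 and *t* in years:

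- observed loss by *t* = m/(λ+m) × [1 − exp(−(λ+m)t)]
- plotted survival = 1 − λ/(λ+m) × [1 − exp(−(λ+m)t)]
- true survival = exp(−λt), which Kaplan-Meier estimates when loss is independent of death

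**Worked case: 5% lost by 36 months.** Solving gives m = 0.02886, so λ+m = 0.40696 and 1 − exp(−3 × 0.40696) = 0.7050. Check on loss: 0.02886/0.40696 × 0.7050 = 0.050. Plotted survival: 1 − 0.3781/0.40696 × 0.7050 = 0.345, against a true 0.322.

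**Range.** The answer depends on when the loss is counted. Each cell gives plotted 36-month survival and median; the truth is 32.2% and 22.0 months.

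| Observed loss | By 61 months, all men followed that long | By a 61-month cutoff with the planned accrual | By 36 months |
|---|---|---|---|
| 3% | 33.3%, 22.36 mo | 33.5%, 22.42 mo | 33.6%, 22.45 mo |
| 5% | 34.0%, 22.62 mo | 34.3%, 22.73 mo | 34.5%, 22.78 mo |
| 10% | 36.0%, 23.35 mo | 36.6%, 23.59 mo | 36.9%, 23.72 mo |

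**Finite-sample check.** In 500 simulated control arms of 400 with about 9.6% lost, Kaplan-Meier at 36 months averaged 32.1% and one minus cumulative incidence 36.4%, against a truth of 32.2%.

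**Between-arm effect, identical survival.** With 3% versus 8% lost by 36 months, the plots read 33.6% and 35.9%: a false gap of 2.4 points before rounding, favouring the arm with more loss. With loss counted by 61 months it is 35.2 − 33.3 = 1.9 points.

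**Between-arm effect, planned benefit.** Under the planned delayed effect, true experimental survival at 36 months is 43.5%, a gap of 43.5 − 32.2 = 11.3 points. With 10% lost in both arms by the 61-month cutoff, the plots read 46.7% and 36.6%, a gap of 10.1. Equal loss therefore raises both curves and slightly narrows a real difference.

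**The case against.** The strongest reply is that nothing inferential depends on this rule. Success rests on the stratified logrank test and the effect size is the stratified Cox hazard ratio. Both censor these men. That stands, and it limits the seriousness of the point.

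A reader might infer more than the documents support:

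- **That the primary result is at risk.** It is not. Type I error, power and the interim boundaries do not depend on which curve is drawn.
- **That planned medians or landmark rates are biased.** SAP 8.2 plans neither. The shifts above apply to whatever a reader takes from the figure.
- **That more than 3% loss is likely.** No rate is given. SAP Appendix A assumes competing events are absent or negligible. Protocol 5.1 adds a vital-status sweep at each monitoring committee meeting, 5.4 requires attempts at contact for survival information, and 7.5 allows late follow-up by telephone. The category is also narrow: definite loss, or withdrawal from vital-status follow-up specifically.
- **That these men are permanently counted as survivors.** Both statuses can be revised, and deaths found later reduce the bias. The figures above allow for no recovery and are high in that respect.
- **That a large gap would show at five years.** At 5.1 years (61.2 months), only men enrolled in the first 1.2 months could have 60 months of follow-up: 3.08 × 1.2² ÷ 2, about 2 of 1,200. The curve carries almost no information there.
- **That the 2.4-point gap would be conspicuous.** The standard error of a between-arm Kaplan-Meier difference at 36 months, under the planned accrual with 400 per arm, is about 3.4 points. The bias is systematic, but in that example it is smaller than the noise.

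Kaplan-Meier has its own condition: it is unbiased only if loss is unrelated to the risk of death. That is a reason to examine informative loss, not to use an estimator that is biased even when loss is independent.

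**Conclusion.** The point holds as a moderate issue of presentation and internal consistency. The SAP's own text shows that the two events are censoring, and the switch replaces a suitable estimate with one biased in a known direction. Under the stated assumptions the overstatement of control survival at 36 months is about 1.1 to 1.4 points just at the trigger, 1.9 to 2.3 points at 5% loss and 3.8 to 4.7 points at 10%. The 22-month median would read about 22.4 to 22.5, 22.6 to 22.8 and 23.3 to 23.7 months respectively. If loss stays at or below 3% in both arms, the rule never operates and there is no effect. The error is confined to the survival figure and anything read from it.

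**What to change.** In SAP 8.2.3, delete the 3% switch and its rationale, and plot Kaplan-Meier in all cases with lost and withdrawn men censored.

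In SAP 3.2.1, 8.2.1 and 8.2.2, relabel definite loss and withdrawal as censoring, and name one censoring date used by both the figure and the test. Protocol 9.1 already points to the date last known alive. Where that differs from the date now used for a competing event, the logrank risk sets could change slightly, so settle the date before unblinding.

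Report loss and withdrawal by arm on the ITT set. SAP section 5 currently summarises disposition on the FAS, which leaves out men randomised but not treated.

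The cost is a short SAP amendment, a simpler figure program and one table. Alpha, power and the event target do not change. A sensitivity analysis for informative censoring would be useful, but it is a separate and optional addition.

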8.2.4. Other Analyses of Survival

The following other analyses, supporting, sensitivity, or exploratory, will be performed:

- Deaths that occur after the cutoff will not be censored.
- Clinical site homogeneity will be assessed by including in the model site grouping multi-level main effect terms and also interaction terms for arm by categorical site grouping.
- The analysis will be re-run with arm by stratum interaction added to the model statement in order to assess arm by stratum interaction. If the 2-sided P value for this multiple degree-of-freedom test of homogeneity is significant at two-sided 0.10, then the stratum-specific hazard ratio estimates and confidence intervals will be computed. If the statistical criterion is not met then the test of homogeneity will be regarded as an exploratory analysis of the data collected. Thus, the outcome of the strata homogeneity test will not affect the interpretation of significance for the primary test, but will affect the way the results are presented or subsequently analyzed.
- Effect modifier analyses will be performed for putatively prognostic factors, including those explored previously in the literature as well as those hypothesized to be predictive in the context of this study. Effect modification will be assessed one factor at a time in stratified models. Each factor will be analyzed as either a natural dichotomy, a dichotomized ordered categorical with cutpoint chosen based on biologic considerations, or a continuous variable dichotomized at the overall median. A separate effect size estimate for arm and its 95% confidence interval will be computed for each level of the dichotomy using contrast statements in SAS.
- The four Kaplan-Meier estimates (arm by factor) for each of the factors analyzed as effect modifiers will be plotted on one graph.
- Regression models with multiple added prognostic covariates will be estimated. The covariates to be added will include those explored previously in the literature as well as those hypothesized to be predictive in the context of this study. Interactions will also be explored for contribution to the model.
- Subjects randomized and not initiating study intervention will be added to the FAS and the primary analyses repeated.
- An analysis of the relationship between dose intensity and outcome by arm will be performed. The main method will be a time-dependent covariate that increases by one for each injection. The interaction between arm and this time-dependent covariate will be the focus of this analysis.

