3.1.4 Exploratory Objectives

To model secondary radiological disease progression over the first year of study participation.

To ascertain whether a greater proportion of subjects randomized to either Arm V+G or Arm V remain event-free (radiological progression) six months post End-of-Treatment visit (using scans at End-of-Treatment visit as a new baseline), as compared to the subjects randomized to Arm P. This analysis will include all subjects, and separately the HLA-A2-expressing subgroup.

To assess the role of post-treatment anti-cancer therapies as an alternative explanation for observed survival differences.

To ascertain whether the survival of HLA-A2-expressing subjects randomized to Arm V+G, or Arm V is superior to that from HLA-A2-expressing-subjects randomized to Arm P.

To ascertain whether a greater proportion of HLA-A2 expressing subjects randomized to Arm V+G or to Arm V remain event-free at six months as compared to the HLA-A2 expressing subjects randomized to Arm P.

To compare arms with respect to immune response to immunizing antigen (PSA), as well as to non-vaccine containing prostate antigens, and tumor-associated antigens, and assess whether immune responses are prognostic and/or predictive.

To evaluate for baseline biomarkers which are prognostic and/or predictive of long term survival outcome.

To compare arms with respect to vaccine effects on circulating tumor cell (CTC) levels (US sites only).

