4.2. Randomization, Stratification, and Blinding

Block randomization will be used to randomly assign subjects in a 1:1:1 manner. Randomization will be stratified according to the following two factors, PSA (equal and above or below 50 ng/ml) and LDH (equal and above or below 200 U/L). These two stratification factors will be used to create a four-level categorical stratification variable for the following combinations of the stratification factors: (PSA < 50 & LDH < 200), (PSA < 50 & LDH ≥ 200), (PSA ≥ 50 & LDH < 200), and (PSA ≥ 50 & LDH ≥ 200). This stratification variable will be used to stratify analyses as specified subsequently.

Unblinding will be performed only in the event of a medical emergency in which the Investigator determines that knowledge of the subject's treatment assignment is necessary for effective treatment. If unblinding is required, the Investigator must contact the Medical Monitor or designee who will record who requested the unblinding, for what purpose, and for which subject, and will notify the DMC in a timely manner.

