8.3.2. Other Analyses of AWE

The following other analyses, supporting, sensitivity, or exploratory, will be performed:

- Clinical site homogeneity will be assessed by including in the model site grouping multi-level main effect terms and also interaction terms for arm by categorical site grouping.
- The analysis will be re-run with arm by stratum interaction added to the model statement in order to assess arm by stratum interaction. If the 2-sided P value for this multiple

degree-of-freedom test of homogeneity is significant at two-sided 0.10, then the stratum-specific hazard ratio estimates and confidence intervals will be computed. If the statistical criterion is not met then the test of homogeneity will be regarded as an exploratory analysis of the data collected. Thus, the outcome of the strata homogeneity test will not affect the interpretation of significance for the primary test, but will affect the way the results are presented or subsequently analyzed.

- Effect modifier analyses will be performed for putatively prognostic factors, including those explored previously in the literature as well as those hypothesized to be predictive in the context of this study. Effect modification will be assessed one factor at a time in stratified models. Each factor will be analyzed as either a natural dichotomy, a dichotomized ordered categorical with cutpoint chosen based on biologic considerations, or a continuous variable dichotomized at the overall median. A separate effect size estimate for arm and its 95% confidence interval will be computed for each level of the dichotomy using contrast statements in SAS.
- Regression models with multiple added prognostic covariates will be estimated. The covariates to be added will include those explored previously in the literature as well as those hypothesized to be predictive in the context of this study. Interactions will also be explored for contribution to the model.
- Subjects who had not been previously observed to have an event and who miss their six month disease assessments are recoded as AWE = 1 (instead of AWE = 0) for both arms, and then for each arm separately.
- Subjects who had not been observed previously to have an event and who have assessment(s) that are not in the window for the six month assessment are coded according to the closest assessment, for both arms, and then for each arm separately.

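### The exploratory effect-modifier analyses (SAP 8.2.4 and 8.3.2) should test continuous factors on a continuous scale and keep the median split for display

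*SAP*

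**What the plan says.** SAP 8.2.4 (Other Analyses of Survival) opens with "The following other analyses, supporting, sensitivity, or exploratory, will be performed". One bullet reads "Effect modifier analyses will be performed for putatively prognostic factors, including those explored previously in the literature", and extends this to factors thought to be predictive in this study. Factors are taken singly, in stratified models. Each must be a natural dichotomy, "a dichotomized ordered categorical with cutpoint chosen based on biologic considerations, or a continuous variable dichotomized at the overall median". The output is described as follows: "A separate effect size estimate for arm and its 95% confidence interval will be computed for each level of the dichotomy". The next bullet plots four Kaplan-Meier curves (arm by factor level) for each factor. No interaction test, significance level or power is given for this analysis.

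SAP 8.3.2 applies the same rule to AWE, again with "a continuous variable dichotomized at the overall median".

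The related objective is in Protocol 3.1.4: "To evaluate for baseline biomarkers which are prognostic and/or predictive of long term survival outcome".

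Four other SAP provisions bear on the point:
- The multivariable-model bullet in 8.2.4 adds "Interactions will also be explored for contribution to the model". It names no factor, scale or criterion.
- The dose-intensity bullet in 8.2.4 keeps the injection count quantitative and makes its interaction with arm the focus.
- Section 8.5.1 specifies an interaction test for HLA-A2, with a criterion of P 0.1 or less. HLA-A2 is binary.
- Sections 8.5.5 and 8.5.7 plan prognostic and explanatory modelling, with no arm-by-factor term specified.

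**The concern.** A predictive factor is one over which the arm effect changes. Cutting a continuous factor at its median treats men just either side of the cut as different, and men at the median and at the far tail as alike. Two things follow. Information about the interaction is thrown away, in an analysis where power is usually low to begin with. And two estimates cannot show whether benefit changes steadily, levels off or appears only beyond some value. The cut is also a property of this sample, so it need not carry over to another population.

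What is at stake is how well the trial can answer an exploratory protocol objective. The primary test, its alpha and the 534-death design do not depend on it.

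**Working it through.** **1. Anchor.** The documents give no power or information figure for any effect-modifier test, so the setting was checked against SAP Table 1 (one-sided 0.0125, HR 0.68, 400 per arm, 22-month control median, 19-month accrual ramp plus 11 months constant, delay of 4 months plus a 4-month ramp).
- Schoenfeld deaths for 90% power without delay: 4(2.241 + 1.282)² / (ln 0.68)² = 334. Freedman's formula gives 343. The SAP has 340.
- Critical HR, exp(−2 × 2.241/√D): 0.784 at 340 deaths and 0.824 at 534. The SAP has 0.784 and 0.823.
- Simulated power for Cases 1 to 4 (4,000 replicates, unstratified logrank): 90.1, 46.1, 85.2 and 98.8%. The SAP has 90.2, 44.5, 86.1 and 98.8%.

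**2. Information kept by a median split.** If the arm-by-X log hazard ratio is linear in X, replacing X by the indicator X > median keeps the squared correlation between the two. That equals (mean absolute deviation from the median / SD)². For a normal X the ratio is √(2/π), so 2/π = 0.637 is kept and 36.3% is lost. In those terms 534 deaths do the work of 534 × 0.637 = 340, and recovering the loss takes π/2 = 1.57 times the events.

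**3. Power after the split.** Power = Φ[(z_α + z_power)√retained − z_α]. Starting from an assumed 80% at two-sided 0.05, with a normal X: Φ[(1.960 + 0.842) × 0.798 − 1.960] = Φ(0.276) = 60.8%. At two-sided 0.10 it is 63.3%. Starting from 90% at two-sided 0.05, it is 73.4%.

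**4. Other distributions**, each with a linear interaction on the scale shown (80% continuous power, two-sided 0.05):

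| Factor | Retained | Lost | Power of split |
|---|---|---|---|
| Normal (or lognormal, linear on log scale) | 0.637 | 36% | 60.8% |
| Uniform | 0.750 | 25% | 67.9% |
| Lognormal, log-SD 0.5, linear on raw scale | 0.516 | 48% | 52.1% |
| Exponential | 0.480 | 52% | 49.3% |
| Lognormal, log-SD 1, linear on raw scale | 0.272 | 73% | 30.9% |

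If the true effect is a step exactly at the median, the split loses nothing and the linear term is the weaker test.

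**5. Simulation check** (800 men, 534 deaths, no delay, unstratified Cox with arm, factor and their product, 1,500 replicates). The effect that gives 80% by formula is 2(1.960 + 0.842)/√534 = 0.2425 per SD, a ratio of hazard ratios of 1.27. This size was chosen to give 80%; it is not in the documents.
- Normal factor: continuous 77.8%, split 57.1%. The gap is 20.7 points, against 80 − 60.8 = 19.2 by formula.
- Uniform factor: continuous 80.1%, split 65.9%.
- Step at the median (0.2425 either side): continuous 59.0%, split 79.2%.

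**6. Effect of stratification.** A simulation with a stratum cut on the same factor gave split power of 61.4% unstratified and 62.2% stratified, and continuous power of 80.2% and 79.8%.

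No corresponding logistic calculation was run for AWE, so the figures apply to survival only.

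**The case against.** The strongest reply is that this is a pre-specified exploratory display. It gives clinicians two readable subgroup estimates and, by fixing the cut in advance, prevents a search for a favourable one. Other routes to interactions exist in 8.2.4 and 8.5. If benefit is confined to one side of a threshold near the median, the split is the better test. All of this is fair. It supports keeping the split and treating the point as minor to moderate. It does not supply the missing analysis: the other routes state no scale, functional form or arm-by-factor term, so for a continuous factor the split is the only concretely specified method. Nothing in the documents suggests thresholds at sample medians.

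Percentiles chosen for reporting also come from the sample. That is true, but the fitted interaction does not depend on them, and the factor values can be printed beside them.

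Four stronger readings that a reader might infer are not supported:
- *That a planned 80%-powered test is cut to about 60%.* No such test or power is planned; both figures are illustrative.
- *That every continuous baseline biomarker in the trial is dichotomised.* The rule governs the one-at-a-time effect-modifier analyses. The multivariable and tertiary models carry no such rule.
- *That PSA and LDH suffer further because the models are stratified.* SAP 4.2 does say "Randomization will be stratified according to the following two factors, PSA (equal and above or below 50 ng/ml) and LDH" (cut at 200 U/L), but strata absorb a factor's main effect. Arm is randomised within strata, so the interaction survives, as step 6 shows.
- *That the 800-man figure covers circulating tumour cells.* The protocol collects these at US sites only, so fewer men contribute.

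**Conclusion.** The point holds as a matter of efficiency and interpretability in exploratory analyses. Every continuous factor in the effect-modifier analyses of SAP 8.2.4 and 8.3.2 is reduced to two halves, with no continuous arm-by-factor analysis specified alongside. For survival, a roughly normal factor and a linear log hazard ratio interaction, about 36% of the information is lost, equivalent to 80% power becoming about 61% at two-sided 0.05. Across the shapes examined the loss runs from none (a step at the median) to about 73% (a strongly skewed factor acting linearly on its raw scale). The 2/pi result is exact under its assumptions. Whether they fit any particular factor is not known from the documents. The primary comparisons, their alpha and the event target are unaffected.

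**What to change.** In SAP 8.2.4 and 8.3.2, for each continuous factor:
- Pre-specify an arm-by-factor interaction with the factor kept continuous (log-transformed if skewed), in the same stratified Cox or logistic model.
- Add a restricted cubic spline version as a check of shape.
- Report the arm effect with 95% CI at chosen factor values, for example the 10th, 50th and 90th percentiles, with those values stated.
- Keep the median-split estimates, and in 8.2.4 the Kaplan-Meier plots, labelled as a display.

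The cost is a few lines of SAP text and code, with no new data. There are two small downsides: a little more analysis to run and read, and a linear term that is less sensitive than the split if the true effect is a threshold near the median. The spline check and the retained split partly cover the second.
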